Statistical Considerations	The study is not powered to test a null hypothesis. A sample size of 40 pediatric PAH subjects aged 7 to 17 years (25 transition [IV/SC Remodulin and inhaled] subjects and 15 de novo prostacyclin subjects) will enable a descriptive evaluation of the PK and an

_

	initial assessment of the safety and tolerability in this subject population for (1) transition from moderate to high doses of IV/SC Remodulin to oral treprostinil, (2) transition from inhaled prostacyclin to oral treprostinil, and (3) initiation of oral treprostinil as add-on therapy in de novo prostacyclin subjects.
	The safety and tolerability of transitioning subjects from IV/SC Remodulin to oral treprostinil (Cohort 1) or from inhaled prostacyclin (Cohort 2) will be based on the percentage of subjects successfully transitioning to oral treprostinil. A successful transition is defined as a subject from Cohort 1 or 2 who is receiving oral treprostinil and no longer receiving IV/SC Remodulin or inhaled prostacyclin, respectively at Week 4 and clinically maintained on oral treprostinil treatment through Week 24. A successful initiation of oral treprostinil (Cohort 3) will be defined as a subject who has been clinically maintained on oral treprostinil through Week 24.
	Analysis of secondary endpoints will be descriptive in nature. Numeric endpoints for post-Baseline assessments will be compared to Baseline using Wilcoxon signed rank test, and p-values will be calculated for descriptive purposes; no formal hypothesis testing is planned.
Sponsor	United Therapeutics Corp. [name]

TABLE OF CONTENTS

LIST	OF CONTACTS FOR STUDY	. 2
INVE	STIGATOR'S AGREEMENT	. 3
PROT	OCOL SYNOPSIS	. 4
TABI	LE OF CONTENTS	11
Table	of In-Text Tables	14
1 B.	ACKGROUND AND RATIONALE	15
1.1	DEFINITION OF CLINICAL PROBLEM.	15
1.2	ORAL TREPROSTINIL BACKGROUND	17
1.2.1	General Pharmacology	17
1.2.2	General Toxicology	18
1.2.3	Clinical Pharmacology	18
1.2.4	Clinical Trials Experience	20
1.3	RATIONALE FOR DEVELOPMENT OF STUDY DRUG IN	
	DISEASE/CONDITION	22
1.4	CLINICAL HYPOTHESIS	23
2 O	BJECTIVES	24
2.1	PRIMARY OBJECTIVE	24
2.2	SECONDARY OBJECTIVES	24
3 E2	XPERIMENTAL PLAN	25
3.1	STUDY DESIGN	25
3.2	OVERALL SCHEDULE OF TIMES AND EVENTS	27
3.3	CLINICAL ASSESSMENTS	34
3.3.1	Efficacy	34
3.3.1 3.3.1.	Efficacy 1 Cardiopulmonary Exercise Testing (CPET)	34 34

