6.1.4 Dosing Interruptions

Subjects must not "make-up" or double-up on missed doses. If dosing is interrupted for longer than 24 hours, consideration should be given to re-titrating the subject's dose gradually to the last dose that was administered prior to the dose interruption, particularly in cases where the last dose prior to interruption was greater than 3 mg. The upward "re-titration" in such instances may, at the Investigator's discretion, be more rapid than the subject's initial dose titration.

In the event of a planned short-term treatment interruption for subjects unable to take oral medications, consider a temporary infusion of SC or IV treprostinil. To calculate the total daily dose (mg) of treprostinil for the parenteral route use the following equation:

Remodulin (ng/kg/min) = (139 x oral treprostinil total daily dose (mg) / weight (kg))

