6.3 COMPLIANCE

Each subject/caregiver will be provided with a dosing diary in order to record dosing information throughout the study. Compliance with oral treprostinil will be assessed at Week 3, 6, 12, and 24/Premature Termination visits, as applicable. At scheduled visits, subjects should be instructed to bring all oral treprostinil to the investigational site.

Upon return of oral treprostinil (study drug) at Weeks 3, 6, 12, 24/Premature Termination, as applicable, the study coordinator or pharmacist must document the number of returned tablets of each strength and determine if the appropriate amount of oral treprostinil remains based upon the dose of oral treprostinil prescribed. Compliance will be determined by comparing the doses that the subject reports taking in their dosing diary to the amount of oral treprostinil returned to the site. Open bottles of oral treprostinil returned at Weeks 3, 6, 12, and 24/Premature Termination will not be re-dispensed to the subject. Any unopened bottles of oral treprostinil may be re-dispensed to the subject and site personnel will dispense additional

new supply of oral treprostinil at Weeks 3, 6, and 12 for the subsequent interval. If necessary, additional oral treprostinil may be dispensed in between protocol-required visits.

Each subject/caregiver will also be asked at each visit whether he or she has been compliant with dosing instructions. Continued non-compliance may lead to withdrawal of the subject from the study, after consultation between the Investigator and the Sponsor.

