## 10.1 TRANSITION TO ORAL TREPROSTINIL

The safety and tolerability of transitioning subjects from IV/SC Remodulin to oral treprostinil (Cohort 1) or from inhaled prostacyclin (Cohort 2) will be based on the percentage of subjects successfully transitioning to oral treprostinil. A successful transition is defined as a subject from Cohort 1 or 2 who is receiving oral treprostinil and no longer receiving IV/SC Remodulin or inhaled prostacyclin, respectively, at Week 4 and clinically maintained on oral treprostinil treatment through Week 24. A successful initiation of oral treprostinil (Cohort 3) will be defined as a subject who has been clinically maintained on oral treprostinil through Week 24. The number (percentage) of subjects who successfully transitioned to oral treprostinil, as well as those who did not successfully transition to oral treprostinil, will be summarized by cohort and overall. The reasons for unsuccessful transition will also be summarized for those subjects who did not successfully transition to oral treprostinil.

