## 11.1 EXTENT OF EXPOSURE

Oral treprostinil dosing will be listed by cohort and subject. The listing will include the date/time of initial oral treprostinil dose, the initial dose (mg), and all subsequent dose changes with start date, morning dose, midday dose, and evening dose.

Remodulin dosing will be listed by subject for Cohort 1 subjects only. The listing will include the initial Remodulin dose (ng/kg/min) and all changes during the study, including the start date/time of the new dose as well as the new dose (ng/kg/min).

Tyvaso dosing will be listed by subject for Cohort 2 subjects only. The listing will include the number of initial Tyvaso breaths per session, the number of initial Tyvaso sessions per day, and all changes during the study; including the start date of new dose, number of breaths per session, and number of sessions per day.

Ventavis dosing will be listed by subject for Cohort 2 subjects only. The listing will include the initial Ventavis dose (X mcg with X mcg/mL), the number of initial Ventavis sessions per

day, and all changes during the study, including the start date of new dose, new dose, and number of sessions per day.

The oral treprostinil dosing and exposure summary will include descriptive statistics for initial oral treprostinil dose, oral treprostinil dose when Remodulin dose is 0.0, oral treprostinil dose at time of hospital discharge, oral treprostinil dose when subject is first off Tyvaso/Ventavis, and final oral treprostinil dose (mg) by cohort. Oral treprostinil dose will be calculated as the sum of the doses administered on a given day divided by the number of doses administered that day. The Remodulin dosing and exposure summary will include descriptive statistics for initial Remodulin dose (ng/kg/min). The Tyvaso dosing and exposure summary will include descriptive statistics for initial Tyvaso breaths per session and a categorical summary of number of initial Tyvaso sessions per day. The Ventavis dosing and exposure summary will include descriptive statistics for initial Ventavis dose per session and a categorical summary of number of initial Ventavis sessions per day.

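### Skipped doses with no recorded event behind them enter neither the success percentage nor any planned summary, and the SAP's dose measure does not change when a dose is missed

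*Protocol*

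**What the plan says.** **Endpoint.** Protocol 10.3.1 and SAP 10.1 base safety and tolerability of transition on a success percentage. Cohorts 1 and 2 must be off the previous prostacyclin at Week 4 and then "clinically maintained on oral treprostinil treatment through Week 24". For Cohort 3, a success is "a subject who has been clinically maintained on oral treprostinil through Week 24" (Protocol synopsis, Statistical Considerations; the same rule stands in SAP 10.1). Neither document defines clinical maintenance or ties it to adherence or interruptions.

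**Compliance.** Protocol 6.3 states: "Compliance with oral treprostinil will be assessed at Week 3, 6, 12, and 24/Premature Termination visits, as applicable". The method is given: "Compliance will be determined by comparing the doses that the subject reports taking in their dosing diary to the amount of oral treprostinil returned". Returned tablets are counted by strength, and families are asked about compliance at each visit. The stated consequence has no threshold: "Continued non-compliance may lead to withdrawal of the subject from the study".

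**Interruptions.** Protocol 6.1.4 gives guidance that begins "If dosing is interrupted for longer than 24 hours" and also covers temporary parenteral treprostinil. It sets up no separate data capture and no link to the endpoint.

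**Dose summary.** SAP 11.1 defines the oral dose as "the sum of the doses administered on a given day divided by the number of doses administered that day". The dosing listing holds the initial dose and later changes, in three daily slots. The lists of tables, listings and figures in SAP 13.1 to 13.3 contain nothing on compliance or interruption.

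**The concern.** In a trial whose primary objective is tolerability, a child may respond to poor tolerance by leaving out doses rather than stopping. Such a child can still be counted as maintained to Week 24. If the skipped doses led to no recorded adverse event, dose change, deviation or withdrawal, they reach no planned summary. The dose table does not help, because a missed dose drops out of both the numerator and the denominator of the SAP formula. A reader of the study report could then see a high success percentage beside a steady dose, with no planned table showing how much drug was taken. The information needed to check this is already gathered at the sites.

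**Working it through.** The documents give no power, alpha or margin for this endpoint (Protocol 10.2), so there is no design figure to reproduce.

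**Inputs**
- 2.5 mg three times daily (TID) and 1.875 mg four times daily (QID), both 7.5 mg a day: Protocol 6.1, example TID-to-QID table. All 12 daily totals in that table check as dose × 3 or dose × 4.
- Dose formula: SAP 11.1.
- 10 to 15 children per cohort: Protocol 10.2.
- Treatment period of 24 weeks = 168 days.

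**1. Missed doses.** Let d be the dose, k the scheduled doses per day and m the number missed.
- SAP dose = (k − m)d / (k − m) = d for any m < k, and 0/0 when m = k.
- Total daily dose = (k − m)d.
- Mean per scheduled dose = (k − m)d / k.

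| Regimen | Missed | SAP dose (mg) | Daily total (mg) | Per scheduled dose (mg) |
|---|---|---|---|---|
| 2.5 mg TID | 0 | 2.5 | 7.5 | 2.50 |
| 2.5 mg TID | 1 | 2.5 | 5.0 | 1.67 |
| 2.5 mg TID | 2 | 2.5 | 2.5 | 0.83 |
| 2.5 mg TID | 3 | undefined | 0 | 0 |
| 1.875 mg QID | 0 | 1.875 | 7.5 | 1.88 |
| 1.875 mg QID | 1 | 1.875 | 5.625 | 1.41 |

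A child on TID dosing who misses one dose every day takes 168 × 2 = 336 of 168 × 3 = 504 doses (66.7%). The SAP dose is the same as for a child who takes all 504.

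**2. Change of regimen.** From 2.5 mg TID to 1.875 mg QID, the SAP dose changes by 1.875/2.5 − 1 = −25.0%, while the daily total stays at 7.5 mg. Across the six rows of the protocol's table the SAP dose falls by 25.0% to 28.6%, while the daily total falls by 0% to 4.8%. The per-dose mean cannot be compared between TID and QID children.

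**3. Weight of one child.** One child in n is 100/n points: 10.0 at n = 10 and 6.7 at n = 15. Exact (Clopper-Pearson) 95% intervals:

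| n | None affected | One affected | Two affected |
|---|---|---|---|
| 10 | 100% (69.2–100) | 90.0% (55.5–99.7) | 80.0% (44.4–97.5) |
| 15 | 100% (78.2–100) | 93.3% (68.1–99.8) | 86.7% (59.5–98.3) |

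**4. Chance that it arises.** The documents give no rate of skipping through intolerance, so a range is assumed. P(at least one) = 1 − (1 − p)^n. For p = 5%, 10% and 20% this is 40%, 65% and 89% at n = 10, and 54%, 79% and 96% at n = 15.

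**The case against.** A reader might infer that intolerance shown as skipped doses is invisible and that the success percentage is biased upward. The documents support neither.

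- **Re-titration after an interruption.** Dose changes go into the eCRF (Protocol 6.1.1 to 6.1.3) and are listed and plotted for each child (SAP 11.1). A recorded re-titration would show as a dip and a climb.
- **Temporary parenteral treprostinil.** It can appear in the Cohort 1 Remodulin listing and plots, or in any cohort among concomitant medications (SAP 9.4.5).
- **Adverse events.** All are listed with action taken (SAP 11.3), and Protocol 15.4 has a category for temporary interruption. Treatment-emergent events and discontinuation reasons are tabulated, and deviations are listed.
- **The dose table.** The listing describes a regimen record, and the table reports dose level at milestones. It does not claim to measure intake.
- **The endpoint.** Clinical maintenance is undefined, so an investigator may already weigh compliance. Missed doses can also have causes other than intolerance.
- **Data.** Protocol 6.3 does not say that diary entries or tablet counts reach the eCRF. If they do, SAP 8 already requires them to be listed.

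All of this stands against the stronger reading, but it does not close the gap. The action-taken field is listed only, Protocol 15.4 keeps only the last action, and no table covers events leading to interruption. Nausea, vomiting and abdominal pain are among the expected disease events that Protocol 9.1.4 keeps out of adverse event recording unless they are serious, unusual or possibly drug-caused. The disease-related event summary (SAP 11.5) specifies no link to dosing. The success rule checks earlier therapy at Week 4 and does not say how a later temporary infusion counts. If the formula runs on regimen records, missed doses never enter it; if it runs on doses taken, they cancel. In neither case do they show.

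**Conclusion.** The point holds as a reporting gap on the primary objective. Skipped doses with no recorded adverse event, dose change, deviation or withdrawal enter neither the success percentage nor any planned summary, and interruptions can be traced only in part. The SAP dose is unaffected by missed doses and is not comparable between TID and QID. Both follow directly from the stated formula.

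The consequence is that tolerability may be overstated. Bias in the primary percentage is not shown: that would require a definition of maintenance that includes adequate intake, which the documents do not give, and a rate of skipping, which they do not report. The size of 6.7 to 10 points per affected child assumes 10 to 15 children per cohort with the whole cohort as denominator; the probabilities in the working rest on assumed rates. The change is worth making before database lock because it is cheap and bears on the main question.

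**What to change.** 1. **SAP 11.1, compliance and interruptions.** Add a summary by cohort and visit interval of compliance (mg taken from tablet counts divided by mg prescribed) and of the number of children with any interruption longer than 24 hours, the interval used in Protocol 6.1.4. Add a table of treatment-emergent adverse events leading to interruption, footnoted that only the last action is recorded.
2. **SAP 11.1, dose.** Report total daily dose in place of, or beside, the per-dose mean, with all four daily doses captured for QID children. Where diary or tablet-count data allow, also show actual intake with missed doses counted as 0.
3. **SAP Table 14.2.1.** Leave the success percentage unchanged. Beside it, show how many successes had an interruption longer than 24 hours, received temporary parenteral treprostinil, or took less than 80% of prescribed mg, with 70% and 90% as alternatives. These cut-offs are proposed here and are not in the documents.

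**Cost.** SAP wording and a few small tables. Tablet counts and interruption dates may have to be entered in the database, since the documents do not clearly place them there; dose-level intake depends on the diaries. The supporting figure may be lower than the headline percentage. No study procedure, dosing rule or clinical rule changes.

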1 BACKGROUND AND RATIONALE

1.1 DEFINITION OF CLINICAL PROBLEM

Pulmonary arterial hypertension (PAH) is defined as an elevation in mean pulmonary arterial pressure (PAPm) greater than 25 mmHg at rest as measured by right heart catheterization (RHC) and is also associated with an increase in pulmonary vascular resistance (PVR). Elevation in PVR causes an increase in right ventricular afterload, impairing right ventricular function and ultimately leading to heart failure and death.

The typical etiologies of PAH include idiopathic (IPAH), heritable (FPAH), or associated with collagen vascular/connective tissue disease, portal hypertension, infection with the human immunodeficiency virus (HIV), history of cocaine or appetite suppressant drug use. Estimates of disease incidence have been reported between 2.4 and 7.6 cases per million individuals [Peacock 2007; Humbert 2006].

There are three major factors thought to contribute to the increased pulmonary vascular resistance seen in this disease: vasoconstriction, remodeling of the vessel wall, and thrombosis. There are a number of metabolic pathways which contribute to these changes that involve vasoactive mediators such as the vasodilators nitric oxide and prostacyclin, and the vasoconstrictor endothelin-1. These substances affect both vascular tone and remodeling leading to their use as pharmacologic targets [Farber, 2004].

PAH occurs in both adults and children. Of the etiological subgroups of PAH, congenital heart disease (CHD) and IPAH are the most common etiologies in pediatric patients [Beghetti, 2008; van Loon, 2011]. For the annual incidence and point prevalence averaged, respectively for IPAH and PAH-CHD, has been estimated at 0.7 and 4.4 (IPAH) and 2.2 and 15.6 (PAH-CHD) cases per million children [van Loon, 2011]. The characteristic pathologic processes of pulmonary vasoconstriction, endothelial dysfunction, vascular remodeling, inflammation, and thrombosis that characterize PAH in adults are also observed in children [Galie, 2009]. Although, more pulmonary vascular medial hypertrophy and a lesser amount of intimal fibrosis and formation of plexiform lesions is observed in children compared to adults [Barst, 2011]. It has also been observed that the prevalence of acute vasoreactivity is

higher in children with IPAH than adults with IPAH, suggesting that vasoconstriction may precede vascular remodeling in this subset of PAH patients [Rosenzweig, 2004; Tissot, 2009].

Clinical symptoms are similar in children and adults, and include exertional dyspnea, fatigue, chest pain and syncope. Syncope and near-syncope presents more commonly in children than adults. Additionally, children appear to tolerate increased workload on the right heart better than in adults, with better preservation of cardiac output and less frequent occurrence of right heart failure with edema [Barst, 2011]. Dyspnea is the most common symptom in older children, occasionally accompanied with chest pain [Rosenzweig, 2004].

Pediatric patients with PAH are currently diagnosed, classified, and treated in the same manner as adults. Treatment efficacy in adults is commonly measured by the change in World Health Organization (WHO) classification or exercise capacity, usually measured as the change in the six minute walk distance (6MWD). Unfortunately, the 6MWD can be difficult to reliably assess in children and may underestimate a child's exercise limitations [Ivy, 2006; Tissot, 2009; Barst, 2011]. Cardiopulmonary exercise testing (CPET) with gas exchange is a complementary non-invasive test to measure functional capacity and better reflect functional status, especially in children with a 6MWD of more than 300 meters [Ivy, 2006; Adatia, 2013; Barst, 2011].

Changes in hemodynamic parameters measured with right heart catheterization can be used to measure treatment efficacy; however, there is increased risk as general anesthesia is required to perform this procedure in the pediatric population [Carmosino, 2007]. Biomarkers, such as brain natriuretic peptide (BNP), have also been positively correlated with disease severity in children and can be used to measure treatment efficacy [Bernus, 2009].

Children with IPAH have a worse prognosis than adults, with an estimated median survival of less than one year. Children also have a shorter length of time between the onset of symptoms and diagnosis [D'Alonzo, 1991; Galie, 2009; Rosenzweig, 2004]. Overall 5-year pediatric PAH survival estimates have been reported between 64% and 81%; although one study reported survival without transplantation or atrial septostomy as 57% [Yung, 2004; van Loon, 2010; Haworth, 2009].

1.2 ORAL TREPROSTINIL BACKGROUND

Prostacyclin is an endogenous substance produced by vascular endothelium with potent vasodilating, antiplatelet aggregation, and antiproliferative properties. Treprostinil (1R,2R,3aS,9aS)-2,3,3a,4,9,9a-Hexahydro-2-hydroxy-1-[(3S)-3-hydroxyoctyl]-1H-benz[f]inden-5-yl]oxy]acetic acid) is a tricyclic benzindene analogue of prostacyclin. Treprostinil is approved as the inhaled (Tyvaso[®]), intravenous (IV)/subcutaneous (SC) (Remodulin[®]) and oral (Orenitram[®]) formulations for the treatment of pulmonary arterial hypertension in adults.

Oral treprostinil is an innovative diolamine salt form of treprostinil formulated as an extended release osmotic tablet for oral administration, and exists in the same biologically active form in the plasma as the inhaled and parental formulations. The tablet core is coated with a semi-permeable membrane and has a laser-drilled aperture through the membrane. Upon contact with water (*e.g.*, after ingestion), the core tablet absorbs water through the semi-permeable membrane. The water dissolves the water-soluble treprostinil diolamine and the water-soluble osmotic excipients, which creates hydrostatic pressure within the membrane, eventually forcing the drug out through the tablet at a controlled rate. Oral treprostinil was recently approved in the United States under the brand name Orenitram for the treatment of pulmonary arterial hypertension WHO Group 1 in adults.

1.2.1 General Pharmacology

The major pharmacological actions of treprostinil are direct vasodilation of pulmonary and systemic arterial vascular beds and inhibition of platelet aggregation. *In vitro*, treprostinil induced concentration dependent relaxation of rabbit isolated pre-contracted mesenteric arteries and inhibition of adenosine diphosphate (ADP) induced platelet aggregation in human and rat platelet rich plasma. In animals, the vasodilatory effects of treprostinil reduce right and left ventricular afterload, also increasing cardiac output and stroke volume. Prostacyclins lower pulmonary artery pressure, increase cardiac output without affecting the heart rate, improve systemic oxygen transport as well as possibly reverse pulmonary artery remodeling. There is also increasing evidence that the ability to block the proliferation of pulmonary artery smooth muscle cells may contribute, along with vasodilation, to the therapeutic effects of

prostacyclins in the treatment of PAH. The mechanism of action is therefore likely to be multifactorial.

